7.3. LOST TO FOLLOW-UP

Site personnel should make reasonable efforts to ensure that all subjects complete the requisite follow up visits. Training cases subjects should complete 1 month follow up and rest of the subjects should complete 24 months follow up. A subject will be considered lost to follow-up if the site has:

1. Attempted to contact the subject with a minimum of two phone calls; and
2. Has mailed a certified letter to the subject with return receipt.

Before a subject is considered lost to follow up, the above described attempts to contact the subject must be documented in the subject's medical records and in the study CRFs.

7.4. STANDARD OF CARE STUDY PROCEDURE

Per an Investigator's decision, subjects may receive concomitant turbinate reduction procedure(s) in addition to placement of the Implants to address other potential causes for the nasal airway obstruction.

There are two commonly used approaches to reduce turbinate size: radiofrequency reduction, and microdebrider-aided resection using a submucosal approach. With this procedure, the lining of the turbinate is left intact, but the tissue from the inside of the turbinate is removed. As the turbinate heals, it becomes smaller than before surgery.

The decision to perform turbinate reductions should be made based on the judgment of the investigator, but should consider the findings of the nasal exam as well as Assessment of Turbinate Hypertrophy Contribution to NAO (see sections 7.2.13 and 7.2.7). Investigators will be instructed to consider concomitant turbinate reductions for any subject for whom the results of these evaluations suggest that turbinate enlargement is contributing to nasal obstruction.

Turbinate reductions procedures are well established and considered standard of care to address respective etiologies. Treatment of the lateral wall with Latera alone or in conjunction with these procedures is being evaluated in this study.

7.5. CONCOMITANT MEDICATIONS, TREATMENTS, AND PROCEDURES

Implant procedure may be completed in conjunction with Turbinate reduction procedure(s).

Current medications related to the treatment of NAO, NVC, and the management of nasal allergies will be documented in the eCRFs.

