4.2.3. EXPLORATORY ENDPOINTS

Exploratory endpoints for informational purposes only:

1. Index procedure resource utilization: Anesthesia, procedure time and time to discharge.
2. Follow up resource utilization: Nasal airway obstruction related return visits and medication utilization.
3. Subject satisfaction questionnaire at 1, 3, and 12 months.
4. Degree of nasal airway obstruction as reported by subjects on the VAS scale at baseline with decongestant use.
5. Endoscopic lateral wall insufficiency score per side²¹ at baseline 1, 3, 6 and 12 months.
6. 3-D camera lateral wall motion assessment per side at baseline and 3, 6, and 12 months (at select sites).
7. Cosmesis changes from baseline evaluated by Independent Photo Review at 3 and 6 months (at select sites).
8. Change in subject sleepiness scale from baseline to 1, 3, 6, and 12 months as reported by subjects on the Epworth Sleepiness Scale (ESS).
9. Allergic rhinitis status at 1, 3, 6, and 12 months.
10. Nasal geometry: length of nose, height and width of nose, skin thickness of lateral wall at baseline.
11. Type of turbinate procedure.

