5. STUDY ENROLLMENT AND WITHDRAWAL

5.1. PARTICIPANT INCLUSION CRITERIA

In order to be eligible to participate in this study, an individual must meet all of the following inclusion criteria:

1. The subject has NOSE Score ≥ 55 .
2. The subject has dynamic lateral nasal wall insufficiency as confirmed by Positive Modified Cottle Maneuver.
3. The subject is ≥ 18 years of age.
4. The subject is willing and able to provide informed consent and comply with the study protocol.
5. The subject is seeking treatment for nasal airway obstruction due to Nasal Valve Collapse (NVC) and is willing to undergo an in-office nasal implant procedure alone or with a turbinate reduction procedure.
6. The subject has appropriate nasal and facial anatomy to receive the Latera Implant.
7. The subject agrees to follow-up examinations through twelve (12) months post operatively.
8. The subject has failed to benefit from appropriate maximal medical management [e.g., nasal steroids (at least 4 weeks); antihistamines; oral decongestants; nasal strips, stents, or cones]. Failure of maximal medical management may be from lack of effectiveness or tolerability.

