7.6. PROHIBITED MEDICATIONS, TREATMENTS, AND PROCEDURES

Concomitant medications or therapies preventing subjects from being eligible to participate in this study are current use of nasal oxygen, CPAP, chronic use of systemic steroids and/or recreational intra-nasal drugs. Additionally, concomitant radiation exposure in the treatment area or chemotherapy will deem a subject ineligible to participate.

In addition, the following treatments will not be permitted concurrent with index procedure or within 24 months after index procedure:

- Functional Endoscopic Sinus Surgery (FESS)
- Sinuplasty procedure
- Rhinoplasty procedure
- Any surgical or non-surgical treatment of the nasal valve, other than the index procedure, within 12 months of the study
- Use of a dilator and/or an external device in the nasal area (e.g. nasal strips).

SPACE LEFT INTENTIONALLY BLANK

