10.2. STATISTICAL HYPOTHESES

Primary Efficacy Endpoint:

- The primary efficacy endpoint is the proportion of treatment responders at 6 months post procedure. Since there is no direct comparison group in this study, the primary efficacy hypothesis is a superiority comparison to a target proportion:

Null Hypothesis H_0 : the proportion of responders at 6 months is = 0.50, versus
Alternative Hypothesis H_A : the proportion of responders at 6 months is $\neq 0.50$

- There are no other formal statistical hypotheses.

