10.4.2. ANALYSIS OF THE PRIMARY EFFICACY ENDPOINT(S)

The primary endpoint will be the proportion of treatment responders at 6 months post procedure. The mITT analysis dataset will be used to analyze the primary endpoint.

Responder is defined as a subject that has at least one (1) NOSE class improvement or at least 20% NOSE score reduction compared to baseline.

Subjects will be classified as non-responders if neither of these criteria is met.

NOSE score is a PRO instrument which measures the impact of nasal obstruction on quality of life. It is scored in increments of 5 points, and the total score is calculated as the sum of all 5 questions multiplied by 5, where the range is 0 (asymptomatic) to 100 (most extreme deleterious impact on quality of life). The NOSE score classes¹⁷ are based on the total calculated score:

- Mild:** 5 – 25 points
- Moderate:** 30 – 50 points
- Severe:** 55 – 75 points
- Extreme:** 80 – 100 points

This primary hypothesis will be evaluated for the mITT using a -2-sided exact test²³, and the corresponding exact (Clopper-Pearson) 2-sided 95% confidence interval will be calculated. The null hypothesis that the proportion of responders is $\neq 0.5$ will be rejected if the p-value is < 0.05 .

Sensitivity analyses will be conducted to determine the impact of missing data on these results. These analyses will depend on the extent of missing data, and will be detailed in the SAP, but may include:

1. Last observation carried forward (LOCF)
2. Subjects with missing data classified as non-responders
3. Re-implanted subjects classified as non-responders

This analysis will be repeated for the Latera stand-alone Population alone. While this study is not sufficiently powered to reject the null hypothesis for this subgroup, the response rate, 95% confidence interval and p-value will be calculated. See section 10.5 for further details.

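### No listed analysis of 6-month response or VAS change accounts for nasal or allergy medication started or increased after the procedure; one added sensitivity analysis would show whether it matters

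*Combined protocol and SAP*

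**What the plan says.** **Medication.** Section 7.5 states that "Current medications related to the treatment of NAO, NVC, and the management of nasal allergies will be documented in the eCRFs". Concomitant medication is a Baseline Visit item (7.1.2, item 5), and changes are recorded at each follow-up visit (7.1.4 and 7.1.5, item 6 in the second).

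**Limits.** The drug limits in 7.6 are worded as eligibility conditions: "Concomitant medications or therapies preventing subjects from being eligible to participate in this study are current use of nasal oxygen, CPAP", followed by chronic systemic steroids and recreational intra-nasal drugs. The separate list for the index procedure and the period after it covers sinus surgery, rhinoplasty, dilators or external devices, and other surgical or non-surgical treatment of the nasal valve. It names no nasal or allergy drug.

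**Entry.** Under 5.1, "The subject has failed to benefit from appropriate maximal medical management", and the failure may be from lack of effect or from intolerance. No stable regimen at baseline is required.

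**Response.** Section 10.4.2: "Responder is defined as a subject that has at least one (1) NOSE class improvement or at least 20% NOSE score reduction compared to baseline". It adds: "Subjects will be classified as non-responders if neither of these criteria is met". The possible sensitivity analyses are LOCF, missing counted as non-response, and "Re-implanted subjects classified as non-responders". Of the 6-month responder test, 10.2 says "There are no other formal statistical hypotheses".

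**Use of the medication data.** Exploratory endpoint 2 in 4.2.3 is "Follow up resource utilization: Nasal airway obstruction related return visits and medication utilization", and 10.4.11 plans a summary of resource use.

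**The concern.** Sections 4.1 and 10.4.1 make each subject their own control. With no comparison arm, a drug started or stepped up between the baseline and 6-month NOSE cannot be told apart from the effect of the procedure. A subject may be off medication at baseline and on it at month 6 without any deviation that the text clearly defines.

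The plan itself treats drugs as able to move the outcome. Section 7.2.13 gives a decongestant at baseline and repeats the obstruction VAS, and congestion is the first NOSE item (7.2.1).

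The responder threshold can also be crossed by a small change. With the classes in 10.4.2, a subject at 55 who falls to 50 moves from severe to moderate, and one at 80 who falls to 75 moves from extreme to severe. Each is 5 points, one step on one item, and each counts as response although 5/55 = 9.1% and 5/80 = 6.3% are well below 20%.

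What is at stake is how the primary response rate and the VAS change can be read. A reader could not tell how much of either was reached under more medication than at baseline.

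**Working it through.** **Inputs.** Sections 10.2, 10.4.2 and 10.5 give the null proportion 0.50, a two-sided exact test at 5%, 150 subjects with 6-month data, an assumed rate of 66%, a cited earlier rate of 80%, and a stand-alone cohort of 50. No document gives the share of subjects who start or increase medication.

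**1. The plan's own figures.** With a null of 0.50 and X the number of responders, the exact two-sided p-value for x above n/2 is 2 × P(X ≥ x | n, 0.50).
- n = 150: 88 responders (58.7%) gives p = 0.041, and 87 gives p = 0.060. The test rejects upward from 88.
- Power at 66% is P(X ≥ 88 | 150, 0.66) = 97.5%, which agrees with the stated >90%.
- n = 50: 33 responders gives p = 0.033, and 32 gives p = 0.065. Exact power at 66% is 56.5%. The normal approximation gives 62.5%, close to the stated 63%.

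**2. Tipping point in the primary test.**
- At 66%: 0.66 × 150 = 99 responders, p = 0.0001. Reclassifying 12 leaves 99 − 12 = 87, or 58.0% (95% CI 49.7% to 66.0%), p = 0.060. Twelve is 8.0% of 150 and 12/99 = 12.1% of responders.
- At 80%: 0.80 × 150 = 120 responders. It takes 120 − 87 = 33 to lose significance, which is 33/120 = 27.5% of responders.

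**3. Power if a share f of responders is reclassified.** Here q = p(1 − f), and power is P(X ≥ 88 | 150, q). The values of f are assumptions.

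| Response rate p | f | q | Power |
|---|---|---|---|
| 66% | 0 | 0.660 | 97.5% |
| 66% | 5% | 0.627 | 86.5% |
| 66% | 10% | 0.594 | 60.7% |
| 66% | 15% | 0.561 | 29.2% |
| 66% | 20% | 0.528 | 8.7% |
| 80% | 10% | 0.720 | >99.9% |
| 80% | 20% | 0.640 | 92.5% |
| 80% | 25% | 0.600 | 66.3% |
| 80% | 30% | 0.560 | 28.3% |

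**4. The other direction.** Suppose the rate without added medication is exactly 50%, and added medication turns a share g of the non-responders into responders, so that q = 0.50 + 0.50g. The chance of an upward rejection is 2.0% at g = 0, 7.6% at 5%, 20.6% at 10% and 42.0% at 15%. These shares are also assumptions.

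**The case against.** Several points on the other side stand.

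- **The medication data are not unused.** A reader might infer that nothing is done with them. The exploratory utilization endpoint and the resource-use summary contradict that. What is missing is a link between medication and response.
- **The drugs are not shown to be wholly unrestricted.** A reader might infer that anything is allowed after the procedure. Section 7.6 bars non-surgical treatment of the nasal valve without saying whether drugs fall under it, so the scope is unclear.
- **The population makes a large drug effect less likely.** Subjects must have a positive modified Cottle manoeuvre, obstruction due to nasal valve collapse and failed medical management. This lowers the risk without removing it, because failure may be from intolerance and the class rule needs only 5 points.
- **Allergy is partly covered.** Section 10.4.8 plans response by time-dependent allergic rhinitis. That is disease status, not drug use.
- **Decongestant appears in one VAS model.** In 10.4.3 it is a covariate for the baseline VAS only, so it does not adjust the change from baseline.
- **Counting outcomes regardless of medication is legitimate.** The objective is to obtain outcomes data, and turbinate reduction is already part of the treatment evaluated. This is a good reason to leave the primary analysis alone.
- **The bias can run either way.** Subjects who improve and cut back their drugs would make the benefit look smaller.
- **The list in 10.4.2 is open.** Section 10.1 leaves further methods to a SAP finalized before database lock, so the gap is in what is listed and can still be closed.

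**Conclusion.** The point holds in a limited form. Sections 7.5 and 7.6 state no limit on starting or increasing nasal-obstruction or allergy drugs after the procedure. Response is defined by NOSE alone, and no listed analysis of response or VAS change takes a change in medication into account. In a self-controlled single-arm trial, drug-assisted improvement therefore counts as response.

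The size is a tipping point: 12 of 99 responders at the assumed 66%, and 33 of 120 at the cited 80%. A reader might infer that the true device rate is lower by some known amount. The documents do not support that, since they give no rate of medication change, and not every subject with added medication would have failed without it. Section 10.5 also presents 66% as a minimum. If the result is near 80%, the test would probably survive and mainly the estimate would shift.

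A reader might also make much of the stand-alone cohort, where 66% of 50 is 33, exactly the rejection limit. That reflects the small cohort, which 10.4.2 and 10.5 already call insufficiently powered, and it says nothing about medication.

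This is a cheap improvement to the analysis plan.

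**What to change.** Leave the primary analysis and the permitted medication unchanged. Add this item to the sensitivity list in 10.4.2, for the mITT and Latera stand-alone populations:

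> Subjects with a nasal-obstruction or allergy medication at the 6-month visit that is new or, where dose is recorded, increased compared with the concomitant-medication record at the Baseline Visit (7.1.2 item 5, section 7.5) are classified as non-responders.

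The comparison should use that baseline record and not the nasal history in 7.2.6. The history covers five years, so a drug stopped before baseline and later resumed could look as if it were already in use. The dose condition is needed because 7.1.5 and 7.5 do not say that dose is recorded at follow-up.

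Two further outputs:
- Tabulate 6-month response by medication increased, unchanged or decreased, which shows possible bias in either direction.
- Run the VAS mixed model in 10.4.3 once without visits under new or increased medication.

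**Cost.** SAP wording, one derived variable from records already planned at baseline and each follow-up, one table and one model run. Subjects who increased medication for an unrelated allergy are scored as failures, so the result is a conservative bound for the changes that are recorded. Dose increases that are not recorded would be missed.

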7.6. PROHIBITED MEDICATIONS, TREATMENTS, AND PROCEDURES

Concomitant medications or therapies preventing subjects from being eligible to participate in this study are current use of nasal oxygen, CPAP, chronic use of systemic steroids and/or recreational intra-nasal drugs. Additionally, concomitant radiation exposure in the treatment area or chemotherapy will deem a subject ineligible to participate.

In addition, the following treatments will not be permitted concurrent with index procedure or within 24 months after index procedure:

- Functional Endoscopic Sinus Surgery (FESS)
- Sinuplasty procedure
- Rhinoplasty procedure
- Any surgical or non-surgical treatment of the nasal valve, other than the index procedure, within 12 months of the study
- Use of a dilator and/or an external device in the nasal area (e.g. nasal strips).

SPACE LEFT INTENTIONALLY BLANK

7.7. SCHEDULE OF STUDY EVENTS

7.7.1. Training Cases - Schedule of Events Table

Study Events	Screening & Enrollment (Visit 1)	Baseline Evaluation (Visit 2) ¹	Treatment (Visit 3) ²	Follow Up 1 Mo/Final Study Visit (Visit 4)	Early Exit
Secure Informed Consent	X				
Inclusion/Exclusion	X		X		
Pregnancy Test ³	X				
NOSE Scale (PRO) ⁴	X	X	X	X	
Modified Cottle Maneuver	X	X			
Demographics & Nasal Medical History	X				
Nasal Exam	X		X		
Photography – Planning Images		X			
NAO Treatment		X			
Concomitant Medications		X	X	X	X
Adverse Event Assessment		X	X	X	X
Complete Study Exit Form					X

¹Visit 2 activities may be done in conjunction with Study Visit 1. In this instance, the Screening NOSE Scale is not required.

² If Visit 3 (Treatment Visit) is more than 1 month after Visit 1, inclusion/exclusion criteria need to be re-confirmed. Additionally, subjects should be asked to review IC form, initial and date the IC document to confirm continued consent for participation, and complete NOSE scale.

³ Female subjects of childbearing potential

⁴ If Visits 1, 2 and 3 are completed on the same day, the Screening and Treatment NOSE Scales are not required.

SPACE LEFT INTENTIONALLY BLANK

7.7.2. Non-Training Cases - Schedule of Events Table

Study Events	Screening & Enrollment (Visit 1)	Baseline Evaluation (Visit 2) ¹	Treatment (Visit 3) ²	Follow Up 1 mo (Visit 4)	Follow Up 3 mo (Visit 5)	Follow Up 6 mo (Visit 6)	Follow Up 12 mo/Final Study Visit (Visit 7)	Follow Up 18 & 24 mo/Final Study Visit (Visits 8 & 9)	Early Exit
Secure Informed Consent	X								
Secure Re-Consent for 18M and 24M Follow Up									
Inclusion/Exclusion	X	X							
Pregnancy Test ³	X	X	X	X	X	X	X	X	
NOSE Scale (PRO)	X	X	X	X	X	X	X	X	
Modified Cottle Maneuver	X	X							
Epworth Sleepiness Scale (PRO)	X		X	X	X	X	X	X	
Subject Satisfaction Questionnaire (PRO)			X	X	X	X	X	X	
Health Economics Questionnaire (PRO)	X		X	X	X	X	X	X	
Demographics & Nasal Medical History	X								
Nasal Exam	X		X	X	X	X	X	X	
Lateral Wall Motion Video	X		X	X	X	X	X	X	
Photography- 3D Camera (select sites)	X			X	X	X	X	X	
Photography -Cosmetic (select sites)	X			X	X	X	X	X	
NAO Breathing Assessment (PRO)	X			X	X	X	X	X	
Assessment of Turbinite Contribution to NAO	X								
Photography - Planning Images			X						
NAO Treatment		X							
Concomitant Medications	X	X	X	X	X	X	X	X	
Adverse Event Assessment	X	X	X	X	X	X	X	X	
Adverse Device Effects Assessment									
Complete Study Exit Form							X ⁵	X	

¹ Visit 2 activities may be done in conjunction with Study Visit 1. In this instance, the Screening NOSE Scale is not required.

² If Visit 3 (Treatment Visit) is more than 1 month after Visit 1, inclusion/exclusion criteria need to be re-confirmed. Additionally, subjects should be asked to review IC form, initial and date the IC document to confirm continued consent for participation, and complete NOSE scale.

³ Female subjects of childbearing potential

⁴ If Visits 1, 2 and 3 are completed on the same day, the Screening and Treatment NOSE Scales are not required.

⁵ To be completed at 24M follow up.

7.8. EARLY TERMINATION VISIT

In the event of an early subject termination, the clinical site should, at a minimum, document Adverse Events and Concomitant Medications changes. Refer to **Section 7.7** Schedule of Events.

8. ASSESSMENT OF SAFETY

8.1. SPECIFICATION OF SAFETY PARAMETERS

All Serious Adverse Events (SAE), Adverse Device Effect (ADE) and Serious Adverse Device Effects (SADE) will be collected and documented through the end of subject participation in the study. In addition, all non-serious device and procedure-related Adverse Events (AE) and all non-serious head and neck, and/or respiratory related AEs will also be collected and documented.

The primary safety endpoint evaluation will consider nasal procedure related and Latera related adverse events through 6 months post-procedure.

The following information for each AE, ADE, SAE and SADE will be collected:

- Date of onset
- Status and/or Outcome
- Date of resolution
- Adverse Event/Effect type (See Section 8.1.1)

In the event of Implant loss or removal, the following information will be documented:

- Implant exposed intranasal at pierce point or exposed on the external skin surface
- Implant retrieved by surgeon or subject
- Whether Implant loss or removal was complete or partial
- SAE or SADE (See Section 8.1.2 and 8.1.3)
- Severity of event (See Section 8.2.1)
- Relation to Study Device and/or procedure (See Section 8.2.2)
- Action taken
- Descriptive narration of Event/Effect

8.1.1. DEFINITION OF ADVERSE EVENTS TYPES

An adverse event (AE) or effect type will be determined by the Investigator. The AE/ADE type should be the categorized by the cause of the AE/ADE and not the action taken to resolve AE/ADE (i.e. foreign body rejection vs implant retrieval).

For consistency of reporting the following list provides guidance as to how AEs are categorized by Spirox. This list does not represent a full list of all possible AE types that could be reported, and is for reference only for consideration in the recording of AE/ADE types in the eCRFs:

- Excessive inflammation
- Significant foreign body sensation
- Excessive pain or discomfort
- Infection

- Foreign body rejection of implants (Extrusion)
- Skin irritation
- Hematoma
- Unintended perforation of the skin
- Intranasal retrieval
- External retrieval

8.1.2. DEFINITION OF ADVERSE EVENTS (AE) AND SERIOUS ADVERSE EVENTS (SAE)

An adverse event (AE) or effect is defined as any untoward and unintended medical occurrence experienced by a clinical study subject. An AE can therefore be any unfavorable and unintended sign, symptom, or disease temporally associated with the use of the investigational product, whether or not related to the product.

The following events will be considered to be serious adverse events (SAE) and must immediately and without delay (within 24 hours) be reported to the study Sponsor by fax and/or email. These events must be reported whether or not the Investigator believes they are related to study procedures, activities or device:

- Death (the investigator will provide a copy of any post-mortem findings, including histopathology reports if available).
- Life-threatening event or injury
- Disability – significant, persistent, or permanent change, impairment, or damage or disruption in the subject's body function/structure, physical activities or quality of life
- Necessitate immediate medical or surgical intervention to:
 - Preclude permanent impairment of a body function or permanent damage to a body structure; or
 - Relieve unanticipated temporary impairment or damage.
- Prolongation of a hospitalization
- Require new hospitalization

